### 8.3 Sample Size Calculation

The main evaluation focus of this project plan is to evaluate whether there is a significant difference in ACE scores of colonoscopy training for endoscopic physicians by using EndoAngel. This project plans to carry out clinical trials in 3 hospitals. According to the literature, we assume that the cognitive score of endoscopists can be increased from 2.5 to 2.8 after intervention, then 126 cases of colonoscopy need to be enrolled, and if the motor score of endoscopists is increased from 2.38 to 2.59, then 350 cases need to be enrolled. Considering the experimental abscission rate of 10%, a total of 385 cases of colonoscopy should be included.

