Study Process:	
1. Subjects meeting all inclusion criteria and those failing all exclusion criteria were included in the study before colonoscopy;
 
2. Include qualified novice doctors for colonoscopy training
 
3. Patients who met the requirements were enrolled and randomly assigned as follows
 
The experimental group: received painless colonoscopy training with the assistance of the artificial intelligence assistant system, which could prompt abnormal lesions and real-time withdrawal speed, and feedback the overspeed percentage.
 
Control group: routine painless enteroscopy training, no special tips.
 
4. After colonoscopy, the teacher scored the colonoscopy using ACE scoring scale

Security	Safety incidents shall be evaluated and reported according to the quality management measures for clinical trials of medical devices

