#### 3.1 Endoscopic physician

➤ Inclusion criteria

Novice colonoscopists without previous experience in independent colonoscopy;

➤ Exclusion criteria

- 1) The number of operating cases does not meet the requirement of sample size
- 2) could not provide informed consent

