## **4 Endpoints**

### **4.1 Primary Endpoint**

- 1) CUSUM learning curve for colonoscopy (ACE scoring scale)
- 2) Average test score difference before and after training

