### **6 Study process**

#### **6.1 Summary of Study Process**

- If the patient meets the inclusion criteria, the patient is invited to participate in the study and then the informed consent procedure for the clinical trial is applied.
- Assess patients' eligibility based on the inclusion/exclusion criteria.
- If the patient meets the inclusion/exclusion criteria, information prior to colonoscopy

will be collected

- If the patient is enrolled, he will be randomized
- colonoscopy is performed after informed consent. Any intraoperative adverse events are recorded on the CRF for submission and subsequent analysis.
- Follow-up will be performed from the postoperative to the study completion, as detailed in the time and event table.

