### **6.3.3 Intraoperative Managements**

- 1) Patient position: prone position with appropriate restraint.
- 2) Insertion route: according to the actual situation of the subject, usually through the anus
- 3) Patients in the control group received colonoscopy without AI assistance, and patients in the experimental group received colonoscopy with AI assistance. The advanced physician carries on the colonoscopy examination under the teacher's guidance.
- 4) After the examination, the teacher scored the colonoscopy according to the ACE scoring scale.

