#### **6.4.2 Replacement**

Subject will be deemed to have commenced the study upon completion of the informed consent process, and any subject who has been discontinued prior to or during the Colonoscopy will not subsequently be replaced by other subjects

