### **6.5 Randomization and Blinding**

#### **6.5.1 Randomization Implementation**

Randomization is conducted according to the study protocol, and the random contents are implemented in an electronic system block-randomized manner (n = 4; experimental group/control group = 1). Randomization prior to Colonoscopy to decide whether to use EndoAngel. The researchers randomized the random results generated by the electronic system, and the generated random results were stored in the research center. The random time (accurate to minute), random person, subject number and acronym were recorded in the corresponding positions of the electronic system.

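### The plan does not say whether a trainee works in one arm or both, and the 385 cases are sized with no allowance for repeated cases by the same trainee

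*Combined protocol and SAP*

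**What the plan says.** **Size.** Section 8.3 needs 126 cases for the ACE cognitive score (2.5 to 2.8) and 350 for the motor score (2.38 to 2.59). It takes the larger and adds for loss: "Considering the experimental abscission rate of 10%, a total of 385 cases of colonoscopy should be included". It gives no SD, significance level, power, ICC, number of trainees or cases per trainee. Under Replacement (the second section numbered 6.4.2), discontinued subjects "will not subsequently be replaced by other subjects".

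**Allocation.** The unit is the patient. Section 6.1 says "If the patient is enrolled, he will be randomized", and 6.5.1 says "Randomization prior to Colonoscopy to decide whether to use EndoAngel". Section 3.3 and the group descriptions in 6.3.3 agree.

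**What the arms are.** The Summary words the experimental arm differently. That group "received painless colonoscopy training with the assistance of the artificial intelligence assistant system", which describes something a trainee receives rather than a patient.

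**Repeated cases.** Section 3.1 excludes a trainee on this ground: "The number of operating cases does not meet the requirement of sample size". The first primary endpoint in 4.1 is a CUSUM learning curve on the ACE scale, which needs successive cases by one operator. The second is "Average test score difference before and after training", which is also measured on the trainee.

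**Analysis.** Section 8.2 lists descriptive summaries, Spearman correlations, an unspecified univariate analysis and a chi-square analysis of adenoma detection by segment score. It contains no between-arm comparison of ACE scores and no term for trainee.

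**The concern.** Section 8.3 makes the ACE score difference the main question, but its case count contains nothing for the fact that one trainee contributes many scores. Scores from one trainee are likely to resemble each other. Whether that harms the comparison depends on something the plan leaves open, namely whether a trainee's cases all fall in one arm or are spread over both.

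With trainees confined to one arm, differences between trainees add to the error of the arm comparison. A test on cases would then reject too often, and a correct test would have less power than a case count suggests. With trainees in both arms, those differences largely cancel, but an outcome that belongs to the whole trainee no longer belongs to an arm. Something in the primary analysis is affected either way, and 8.2 gives no model to settle the matter.

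Separately, adding 10% to 350 does not leave 350 after a 10% loss.

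**Working it through.** **Step 1. Reproduce 385.** Inputs from 8.3: 350 cases and 10% loss.
- 350 × 1.10 = 385, the plan's figure.
- 385 × 0.90 = 346.5, so about 346 remain if the full 10% is lost and not replaced.
- 350 / 0.90 = 388.9, so 389, which is 4 more than 385.

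**Step 2. What 350 and 126 imply.** This assumes a two-sided 5% level and 1:1 allocation, since 8.3 states neither level nor power. For 80% power, n per arm = 2(1.96 + 0.8416)²/d², where d is the standardised difference.
- d = 0.3: 174.4 per arm, total 350. With the motor difference of 0.21, the SD is 0.70.
- d = 0.5: 62.8 per arm, total 126. With the cognitive difference of 0.30, the SD is 0.60.

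Both figures fit a formula that treats every case as independent. The fit is not unique: 350 at 90% power corresponds to d of about 0.347.

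**Step 3. Cost of the inflation step.** With d = 0.3 and a t-test, power is 79.9% at 350 cases and 79.5% at 346, about 0.4 points.

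**Step 4. Each trainee in one arm (no section states this).** The number of trainees k and the ICC are assumptions. With 346 cases, the design effect is DE = 1 + (346/k − 1) × ICC. Power uses a noncentral t with k − 2 degrees of freedom and noncentrality d√(346/(4·DE)). The type I error of a naive case-level test is 2[1 − Φ(1.96/√DE)].

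| k | ICC | DE | Power if 350 reflects 80% | Power if 350 reflects 90% | Naive type I error |
|---|---|---|---|---|---|
| 24 | 0.02 | 1.27 | 66% | 78% | 8% |
| 12 | 0.05 | 2.39 | 37% | 47% | 21% |
| 6 | 0.10 | 6.67 | 13% | 16% | 45% |

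Part of the loss comes from the few degrees of freedom. With ICC = 0 in the 80% column, power is already 76% for 24 trainees and 56% for 6.

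**Step 5. Each trainee in both arms, no carry-over, the same AI effect in every trainee.** With arms balanced within trainee, the cases needed are 350 × (1 − ICC): 343 at ICC 0.02 and 315 at ICC 0.10. A naive standard error is too wide by 1/√(1 − ICC) − 1, that is 1.0% to 5.4%. In a simulation of 3,000 runs (blocks of 4 in 3 hospitals, not stratified by trainee, 346 cases, 80% nominal), power with trainee modelled was 78% (24 trainees, ICC 0.02) and 83% (6 trainees, ICC 0.10).

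**Step 6. The test score.** Its information is the number of trainees. The smallest differences detectable at 80% power, two-sided 5%, in SDs of the change score, are:
- between two equal arms: 1.20 (24 trainees), 1.80 (12), 3.07 (6);
- before/after in all trainees: 0.60, 0.89, 1.43.

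The number of colonoscopies does not enter.

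**The case against.** Every operative allocation sentence is patient by patient, so the literal reading puts trainees in both arms. On that reading the ACE comparison is adequately sized and naive error bars are slightly conservative. This stands, and it is why the low powers in step 4 are conditional. A reader might infer from them that 385 is too small. The documents do not support that: it needs a nested design that no section states, plus an assumed trainee number, ICC and nominal power. The Summary's description of the arms as training keeps nesting open but does not establish it.

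The inflation slip is immaterial, and adding 10% is a common convention. This also stands. A reader might infer that 346 is what the analysis will have, but it is the worst case. Section 6.4 keeps data from before discontinuation, and 8.4 keeps dropouts in the FAS and does not automatically remove them from the PP set, on which the main analysis rests. Scoring is also immediate: "After the examination, the teacher scored the colonoscopy according to the ACE scoring scale". A case could therefore be discontinued and still carry a score.

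A reader might also infer that a trainee random intercept gives valid error bars under either design. It does not. With trainees in both arms and an AI effect that varies between trainees (assumed SD 0.2 of the score SD), type I error is about 7% with 24 trainees and 12% with 6. A random intercept does not represent the expected trend with case number, and it cannot remove bias from learning carried from AI cases into control cases.

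**Conclusion.** The point holds as a gap in design and analysis and should be fixed. The plan does not state a trainee's arm, makes no allowance for repeated cases and names no between-arm ACE comparison. None of this depends on assumed figures.

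The consequence depends on the missing statement. With trainees in both arms and no carry-over, the ACE comparison is sound in size, but the test score and a whole-trainee CUSUM curve mix the arms. With trainees in one arm, the loss could be large, over the assumed ranges in step 4. Under either design, 385 supports the comparison of mean ACE scores only.

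The inflation step is a minor remark: 4 cases, about 0.4 power points at an assumed 80%. Confidence is medium, because the size of the main effect rests on quantities that the documents do not give.

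**What to change.** - **6.5.1:** state whether each trainee works in one arm or both.
- **8.2:** add that ACE scores are compared between arms in a linear mixed model with a trainee random intercept, a case-order term and small-sample degrees of freedom. Add a trainee-by-arm random effect if trainees work in both arms. Note that the model does not remove carry-over of learning.
- **8.3:** keep 385 and state that about 346 evaluable cases are expected in the worst case, or restate the target as 389. Say that 385 supports the ACE mean-score comparison only, and that the information for the test score is the number of trainees.
- **If each trainee works in one arm:** restate power in 8.3 over a range of ICCs and trainee numbers.
- **If trainees work in both arms:** state that the test score and the whole-trainee CUSUM curve are not between-arm comparisons.

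The cost is wording in three sections and, if trainees work in one arm, one recalculation. No patients are added if 385 is kept, and 4 if 389 is chosen. The downside is that the stated power may become less favourable.

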### 8.4 Statistical analysis set

All patients who met the inclusion and exclusion criteria were considered eligible for recruitment.

The two analysis sets in this study are defined as follows:

- The full analysis set (FAS) population analysis set will contain all eligible cases and shedding cases, but does not include culling cases.
- The Compliance (PP) population analysis set will include all subjects in the FAS analysis set with no significant deviation from the program.

Intention-to-treat and conformity analysis sets should be used to analyze the primary efficacy endpoints. The main analysis will be based on the PP analysis set. FAS analysis was regarded as supportive analysis.

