### **3.3 Definition of enrollment**

After participants signed informed consent, they were randomized before colonoscopy. The randomization time was the enrollment time, and was recorded in CRF.

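### Section 8.4 makes the per-protocol set the main analysis of a difference question, so events after randomisation can select the case-level ACE comparison

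*Combined protocol and SAP*

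**What the plan says.** - **Ranking of the sets (8.4).** "The main analysis will be based on the PP analysis set. FAS analysis was regarded as supportive analysis". The sentence before it reads: "Intention-to-treat and conformity analysis sets should be used to analyze the primary efficacy endpoints".
- **Definition of FAS (8.4).** The full analysis set "will contain all eligible cases and shedding cases, but does not include culling cases". Culling is not defined.
- **Definition of PP (8.4).** The per-protocol set "will include all subjects in the FAS analysis set with no significant deviation from the program". The section does not say what makes a deviation significant, who decides, when, or whether that person knows the arm.
- **Question asked (8.3).** The main focus is "to evaluate whether there is a significant difference in ACE scores of colonoscopy training for endoscopic physicians by using EndoAngel". Planned increases are 2.5 to 2.8 (cognitive) and 2.38 to 2.59 (motor). No non-inferiority or equivalence margin appears anywhere.
- **Time of randomisation.** Section 3.3: "After participants signed informed consent, they were randomized before colonoscopy". Section 6.5.1: "Randomization prior to Colonoscopy to decide whether to use EndoAngel".
- **Withdrawal after randomisation.** Section 6.4.2 (Intraprocedure) lists reasons to withdraw a subject during the examination. They include non-use of the specified instrument and failure to complete the colonoscopy. Section 6.4 keeps data gathered before discontinuation, and 6.4.2 (Replacement) rules out replacing discontinued subjects.
- **Time of scoring (6.3.3).** The teacher gives the ACE score once the examination is over.

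**The concern.** For a difference question, the usual lead analysis keeps everyone in the arm to which they were randomised, because only that comparison is protected by the randomisation. A PP set removes cases for what happened later. If those cases differ between the arms in number or in score, the PP difference mixes the effect of the system with the effect of the selection.

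The plan offers plausible routes for this. Non-use of the instrument is tied to the arm. Section 7.5 foresees software faults, after which the doctor carries on unaided; that can happen only in AI-assisted cases. An incomplete examination may be related to the score, since ACE rates that same examination. With membership of PP undefined, nothing prevents such cases from being dropped after the results are known, and if PP and FAS disagree, 8.4 lets PP lead.

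**Working it through.** **1. The plan's own figures.** Planned differences are 2.59 - 2.38 = 0.21 (motor) and 2.8 - 2.5 = 0.30 (cognitive). The inflation step reproduces: 350 x 1.10 = 385; dividing by 0.90 gives 389. The base figures of 126 and 350 cannot be reproduced, because alpha, sidedness, power and SD are not stated. No figure in the plan tests the choice of set.

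**2. Can randomised cases leave PP?**
- Randomisation comes first (3.3, 6.5.1) and withdrawal can follow (6.4.2 Intraprocedure).
- Section 6.4 names serious deviation alongside withdrawal, and PP drops significant deviations. The natural reading is that withdrawn cases can leave PP.
- No sentence says so outright. Section 6.4 keeps their earlier data, and FAS keeps shedding cases. The step is therefore an inference.

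**3. How far could the difference move?** The documents give no exclusion rates by arm, so every input here is an assumption. The model covers mean ACE score only. Let q be the share of an arm's scored cases that PP excludes, and gap the amount by which excluded cases score below retained ones (the same in both arms). Then:

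- mean of all scored cases in an arm = retained mean - q x gap
- PP difference minus difference in all scored cases (AI minus control) = (q_AI - q_control) x gap

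If PP excludes share p of randomised cases and share s of those have a score, q = p x s / (1 - p x (1 - s)).

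Take p = 5% (AI) and 10% (control):

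- s = 1: q = 0.05 and 0.10, a difference of -0.05.
- s = 0.5: q = 0.025/0.975 = 0.0256 and 0.05/0.95 = 0.0526, a difference of -0.0270.
- s = 0: no excluded case has a score, so the shift is 0.

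| Gap (points) | Shift, half scored | % of 0.21 | Shift, all scored | % of 0.21 |
|---|---|---|---|---|
| 0.25 | -0.0067 | 3.2% | -0.0125 | 6.0% |
| 0.5 | -0.0135 | 6.4% | -0.025 | 11.9% |
| 1.0 | -0.0270 | 12.9% | -0.050 | 23.8% |

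Against the cognitive difference of 0.30, the largest shift is 0.050/0.30 = 16.7%. Equal exclusions with the same gap and s give zero. Swapping the arms reverses the sign: PP understates the effect if control loses more low-scoring cases and overstates it if the AI arm does.

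**4. Is the gap plausible?** Assume two arms of 175 and a two-sided 5% test. The implied motor SD is 0.21 x sqrt(175/2)/(1.960 + 0.842) = 0.70 at 80% power, or 0.21 x sqrt(175/2)/(1.960 + 1.282) = 0.61 at 90%. A gap of 0.25 is about 0.4 SD. A gap of 1.0 is 1.4 to 1.7 SD, which is large.

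**The case against.** **The intention-to-treat label.** A reader might infer that an undefined intention-to-treat set adds to the bias. The text does not support that. Section 8.4 defines two sets, names two for the primary endpoints and ranks two, and the abbreviation list in section 10 expands ITT and PP but not FAS. Intention-to-treat probably means FAS. This needs a label clarification and is not a source of bias.

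**FAS may already be close to what is wanted.** Section 8.4 links eligibility to the entry criteria, so culling may mean only ineligible cases. That is possible but not stated, and PP would still lead.

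**The link to the primary endpoints is partial.** Section 4.1 names a CUSUM learning curve and a before/after test-score difference. The second appears to be measured on trainees, so dropping patient cases need not affect it. Section 8.2 gives no between-arm ACE test, so the mean difference modelled above is one reading, drawn from 8.3. This objection stands and limits the point to the case-level ACE comparison.

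**The size is assumed.** A reader might take the upper rows of the table as the expected bias. They need a large gap and many scored exclusions, and an aborted case may have no score. Nor does the 10% loss figure ("Considering the experimental abscission rate of 10%, a total of 385 cases of colonoscopy should be included") fix a PP exclusion rate: it may describe shedding cases, which FAS keeps. Most of the withdrawal reasons in 6.4.2 have no evident link to arm; non-use of the instrument is the clear exception.

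**FAS is reported anyway.** It would reveal the effect of excluding scored cases. It cannot do so for cases without a score, and it ranks second.

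**Conclusion.** The concern holds as a flaw in how the sets are ranked and defined. PP leads on a difference question, and two undefined terms leave its membership open to events after randomisation. It should be fixed.

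The documents do not show that bias will occur, or which arm it would favour. Under the stated assumptions the shift in mean ACE difference runs from zero, through 0.007 to 0.0125 (3% to 6% of 0.21) with a modest gap, to 0.05 (24%) in the most unfavourable case shown. Zero for unscored cases means only that the choice of set changes nothing; missing scores could still bias either analysis. The illustration treats colonoscopies as independent and does not extend to the CUSUM curve or the test-score endpoint. Confidence is high on what 8.4 says and low on the size of the consequence.

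**What to change.** In 8.4:

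1. Make all randomised cases, analysed in the assigned arm, the main analysis for the case-level ACE comparison, with PP supportive.
2. Limit culling to eligibility failures established from pre-randomisation data without knowledge of arm.
3. Define significant deviation before unblinding, and report PP exclusions and their reasons by arm.
4. State whether intention-to-treat means this set or FAS.
5. State that the test-score endpoint appears to be measured on trainees, so the patient-case set does not define its population.

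In 8.2, state how randomised cases without an ACE score are handled, with one sensitivity analysis. Without this, changing the set does nothing for those cases.

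The cost is wording in two sections and a little more analysis work, with no extra patients. The estimated effect may be somewhat smaller if the system is not used in some assigned cases. Rules on when a procedure is stopped are unchanged.

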## 9 Device Description

EndoAngel

Version:EA2301

## 10 Abbreviations

Abbreviations	Full Name	Chinese
AE	Adverse Event	不良事件
CFDA	China Food and Drug Administration	国家食品药品监督管理总局
CNDA	China National Drug Administration	国家食品药品监督管理总局
CRF	Clinical Record File	病例报告表
CTCAE	Common Terminology Criteria for Adverse Events	不良事件常规评价标准
EC	Ethical Committee	伦理委员会
ICD	Informed Consent Document	知情同意文件
ICF	Informed Consent Form	知情同意书
ITT	Intention to Treat	意向治疗分析集
PP	Per Protocol	符合方案集
SAE	Serious Adverse Event	严重不良事件
